### 11.1 Adverse Events

#### 11.1.1 Reportable AEs

11.1.1.1 All AEs that occur after the informed consent is signed and baseline assessments are completed (including run-in) through the day preceding the day of surgery must be recorded on the AE CRFs (paper and/or electronic) whether or not related to study agent.

11.1.1.2 AEs not related to surgery that occur from the day of surgery through the post vaccination follow-up visit (30 days $\pm$ 7 days post-op) must be recorded on the AE CRF (paper and/or electronic) whether or not related to study agent.

11.1.1.3 All SAEs, including all hospitalizations, during the study period will be reported as per DCP SAE reporting procedures, with the following exception:

Hospitalization for planned surgery will not be reported. However, if this hospitalization event lasts longer than the usual period at the institution (as determined by the Site Principal Investigator or Sponsor), it will be reportable as an SAE. Adverse events (AEs) relevant to the prolongation of this hospitalization will also be collected and reported on AE CRFs.

#### 11.1.2 AE Data Elements:

The following data elements are required for adverse event reporting.

- AE verbatim term

- System Organ Class (SOC)
- Common Terminology Criteria for Adverse Events v4.0 (CTCAE) AE term
- Event onset date and event ended date
- Severity grade
- Attribution to study agent (relatedness)
- Whether or not the event was reported as a serious adverse event (SAE)
- Whether or not the subject dropped due to the event
- Outcome of the event

### 11.1.3 Severity of AEs

11.1.3.1 Identify the AE using the NCI Common Terminology Criteria for Adverse Events (CTCAE) version 4.0. The CTCAE provides descriptive terminology and a grading scale for each adverse event listed. A copy of the CTCAE can be found at [http://ctep.cancer.gov/protocolDevelopment/electronic\\_applications/ctc.htm](http://ctep.cancer.gov/protocolDevelopment/electronic_applications/ctc.htm)

AEs will be assessed according to the CTCAE grade associated with the AE term. AEs that do not have a corresponding CTCAE term will be assessed according to the general guidelines for grading used in the CTCAE v4.0. as stated below.

#### CTCAE v4.0 general severity guidelines:

Grade	Severity	Description
1	Mild	Mild; asymptomatic or mild symptoms; clinical or diagnostic observations only; intervention not indicated.
2	Moderate	Moderate; minimal, local or noninvasive intervention indicated; limiting age-appropriate instrumental activities of daily living (ADL)*.
3	Severe	Severe or medically significant but not immediately life-threatening; hospitalization or prolongation of hospitalization indicated; disabling; limiting self-care ADL**.
4	Life-threatening	Life-threatening consequences; urgent intervention indicated.
5	Fatal	Death related to AE.

#### ADL

\*Instrumental ADL refers to preparing meals, shopping for groceries or clothes, using the telephone, managing money, *etc.*

\*\*Self-care ADL refers to bathing, dressing and undressing, feeding self, using the toilet, taking medications, and not bedridden.

### 11.1.4 Assessment of relationship of AE to treatment

The possibility that the adverse event is related to study agent will be classified as one of the following: not related, unlikely, possible, probable, definite.

### 11.1.5 Follow-up of AEs

All AEs, including lab abnormalities that in the opinion of the investigator are clinically significant, will be followed according to good medical practices and documented as such.

Unresolved AEs with a “possibly”, “probably” or “definitely” attribution to study agent at the post vaccination follow-up visit will be managed according to good medical practices and documented as such with a minimum of a telephone call to follow-up on resolution at 20-30 days after the post vaccination follow-up visit.

## 11.2 Serious Adverse Events

11.2.1 DEFINITION: Fed. Reg. 75, Sept. 29, 2010 defines SAEs as those events, occurring at any dose, which meet any of the following criteria:

- Results in death
- Is life threatening (*Note: the term life-threatening refers to an event in which the participant was at risk of death at the time of the event; it does not refer to an event which hypothetically might have caused death if it were more severe*).
- Requires inpatient hospitalization or prolongation of existing hospitalization
- Results in persistent or significant incapacity or substantial disruption of the ability to conduct normal life functions
- Is a congenital abnormality/birth defect
- Important medical events that may not result in death, be life-threatening or require hospitalization may be considered serious when, based upon appropriate medical judgment, they may jeopardize the patient or subject and may require medical or surgical intervention to prevent one of the outcomes listed.

### 11.2.2 Reporting SAEs to DCP

11.2.2.1 The Lead Organization and all Participating Organizations will report SAEs on the DCP SAE form found at

<https://prevention.cancer.gov/clinical-trials/clinical-trials-management/protocol-information-office/pio-instructions-and-tools/2012-consortia>.

11.2.2.2 Reporting within 24 hours of knowledge of the event.

11.2.2.2(A) Report to the NCI DCP Medical Monitor within 24 hours:

Contact the DCP Medical Monitor by email or phone within 24 hours of knowledge of the event.

[name], MD  
NCI/Division of Cancer Prevention  
[name]  
[name]  
[name]  
[name]  
[contact]  
[[contact]](mailto:[contact])

Include the following information when emailing / calling the Medical Monitor:

- Date and time of the SAE

- Date and time of the SAE report
- Name of reporter
- Call back phone number
- Affiliation/Institution conducting the study
- DCP protocol number
- Title of protocol
- Description of the SAE, including attribution to drug and expectedness

11.2.2.2(B) Report to the Consortium Lead Organization (CLO) ([name] or designee) within 24 hours of knowledge of the event:

The same information reported to the DCP Medical Monitor should be provided to the Consortium PI, [name] or the CLO Coordinator ([name]) via email, phone or fax within 24 hours of knowledge of the event. The contact details are provided on the cover page of this protocol.

11.2.2.3 Reporting within 48 hours of knowledge of the event:

11.2.2.3 (A) Email the written SAE reports to the DCP Medical Monitor within 48 hours of learning of the event using the paper SAE form. The SAE forms should be obtained at [https://prevention.cancer.gov/sites/default/files/uploads/clinical\\_trial/SAE-Form\\_05-02-2016.pdf](https://prevention.cancer.gov/sites/default/files/uploads/clinical_trial/SAE-Form_05-02-2016.pdf).

11.2.2.3 (B) The written SAE reports will also be sent to DCP's Regulatory Contractor, CCS Associates, at [[contact]](mailto:[contact]).

11.2.2.3 (C) The written SAE report will also be emailed to the CLO PI ([name]), or faxed to [contact].

It is the responsibility of the CLO to inform the Protocol Principal Investigator upon receipt of the report from the organization experiencing the event.

11.2.2.4 The DCP Medical Monitor and regulatory staff will determine which SAEs require FDA submission.

11.2.2.5 The Lead Organization and all Participating Organizations will comply with applicable regulatory requirements related to reporting SAEs to the IRB/IEC.

11.2.2.6 Follow-up of SAE

Site staff should send follow-up reports as requested when additional information is available. Additional information should be entered on the DCP SAE form in the appropriate format. Follow-up information should be sent to DCP as soon as available. SAEs related to the study agent will be followed until resolved.

## **12. STUDY MONITORING**

### **12.1 Data Management**

This study will report clinical data using the Data Management Initiative (DMI) web-based application managed by the Consortium Biostatistics and Data Management Core. Data Management Initiative (DMI) infrastructure has been developed in the Division of Quantitative Sciences (DQS), MD Anderson Cancer Center. This infrastructure supplies integrated database and software services for web-based data collection, randomized treatment assignment, reporting, query, data download, and data quality management. The DMI will be the database of record for the protocol and subject to NCI and FDA audit. All DMI users will be trained to use the DMI system and will comply with the instructions in the protocol-specific “DMI User Manual” as well as applicable regulatory requirements such as 21 CFR; Part 11. Data management procedures for this protocol will adhere to the Data Management Plan (DMP) on file at the DCP for contract HHSN261201200034I.

### **12.2 Case Report Forms**

Participant data will be collected using protocol-specific case report forms (CRF) developed from the standard set of DCP Chemoprevention CRF Templates and utilizing NCI-approved Common Data Elements (CDEs). The approved CRFs will be used to create the electronic CRF (e-CRF) screens in the DMI application. Site staff will enter data into the e-CRF. Amended CRFs will be submitted to the DCP Protocol Information Office for review and approval. Approved changes will be programmed into the DMI database by the Consortium Biostatistics and Data Management Core.

### **12.3 Source Documents**

Source documentation will include only those documents containing original forms of data, including clinic charts, shadow files, hospital charts, and physician notes. Data recorded directly on the CRFs designated as source documents (*i.e.*, no prior written or electronic record of data) will be considered source data. All other data recorded on the CRFs will not be considered source documentation.

### **12.4 Data and Safety Monitoring Plan**

The Data and Safety Monitoring Plan for the MD Anderson Consortium is on file at the DCP. This study will be monitored by the MDACC Data and Safety Monitoring Board (DSMB), the data and safety monitoring board of record for this study. The DSMB reports to the President, or his designee, as the on-campus representative of The University of Texas Board of Regents. It oversees the data and patient safety issues for randomized clinical trials that originate at MD Anderson; that are coordinated or analyzed by MD Anderson and are not being monitored by any other DSMB; or have been designated as requiring DSMB monitoring at the request of the IRB, the CRC, or institution. The primary objectives of the DSMB are to ensure that patients' rights pertaining to participation in a research study are protected, and that patients' interests are prioritized over the interests of the scientific investigation. Responsibilities include:

- (a) Review interim analyses of outcome data (prepared by the study statistician or other responsible person at the time points defined in the study) approved by the IRB and additional time points as determined by the DSMB, and to recommend, if necessary, whether the study needs to be changed or terminated based on these analyses;
- (b) Determine whether, and to whom, outcome results should be released prior to the reporting of study results;

- (c) Review interim toxicity data and efficacy of treatment;
- (d) Review major research modifications proposed by the investigator or appropriate study committee prior to implementation (*e.g.*, termination, dropping an arm based on toxicity results from the study or results of other studies, increasing target sample size).

Refer to the Data and Safety Monitoring Plan for the MD Anderson Consortium on file at the DCP for further details.

## **12.5 Sponsor or FDA Monitoring**

The NCI, DCP (or their designee), pharmaceutical collaborator (or their designee), or FDA may monitor/audit various aspects of the study. These monitors will be given access to facilities, databases, supplies and records to review and verify data pertinent to the study.

## **12.6 Record Retention**

Clinical records for all participants, including CRFs, all source documentation (containing evidence to study eligibility, history and physical findings, laboratory data, results of consultations, *etc.*), as well as IRB records and other regulatory documentation will be retained by the Investigator in a secure storage facility in compliance with Health Insurance Portability and Accountability Act (HIPAA), Office of Human Research Protections (OHRP), Food and Drug Administration (FDA) regulations and guidances, and NCI/DCP requirements, unless the standard at the site is more stringent. The records for all studies performed under an IND will be maintained, at a minimum, for two years after the approval of a New Drug Application (NDA). For NCI/DCP, records will be retained for at least three years after the completion of the research. NCI will be notified prior to the planned destruction of any materials. The records should be accessible for inspection and copying by authorized persons of the Food and Drug Administration. If the study is done outside of the United States, applicable regulatory requirements for the specific country participating in the study also apply.

## **12.7 Cooperative Research and Development Agreement (CRADA)/Clinical Trials Agreement (CTA)**

The agent(s) supplied by DCP, NCI, used in this protocol, is/are provided to the NCI under a Collaborative Agreement (CRADA, CTA, MTRA) between SELLAS (hereinafter referred to as Collaborator(s)) and the NCI Division of Cancer Prevention. Therefore, the following obligations/guidelines, in addition to the provisions in the “Intellectual Property Option to Collaborator(s)” contained within the terms of award, apply to the use of Agent(s) in this study:

12.7.1 The Research Material will only be used for research purposes by Recipient, its contractors, and agents and Investigator for the Research Project described in Attachment A, under suitable containment conditions. This Research Material will not be used for any other purpose including but not limited to commercial purposes for screening, production or sale, for which a commercialization license may be required. DCP and its Investigator shall not use the Research Material in assays for the identification of potential commercial products. At the end of the Research Project, Recipient and its Investigator will be responsible for ensuring the return of any unused Research Material to Sponsor, unless otherwise directed by Sponsor. Collaborator(s) data for Agent(s) are confidential and proprietary to Collaborator(s) and shall be maintained as such by the investigators. The protocol documents for studies utilizing investigational agents contain confidential information and should

not be shared or distributed without the permission of the NCI. If an individual participating on the study or participant's family member requests a copy of this protocol, the individual should sign a confidentiality agreement. A suitable model agreement can be downloaded from the DCP website.

12.7.2 Each Collaborator shall agree to permit use of the Multi-Party Data from the clinical trial by any other Collaborator solely to the extent necessary to allow said other Collaborator to develop, obtain regulatory approval, or commercialize its own investigational agent.

12.7.3 Any Collaborator having the right to use the Multi-Party Data from these trials must agree in writing prior to the commencement of the trials that it will use the Multi-Party Data solely for development, regulatory approval, and commercialization of its own investigational agent.

12.7.4 Clinical Trial Data and Results and Raw Data developed under a collaborative agreement will be made available exclusively to Collaborator(s), the NCI, and the FDA, as appropriate. All data made available will comply with HIPAA regulations.

12.7.5 When a Collaborator wishes to initiate a data request, the request should first be sent to the NCI, who will then notify the appropriate investigators of Collaborator's wish to contact them.

12.7.6 Any abstract or manuscript reporting the results of this clinical trial must be provided to DCP for immediate delivery to Collaborator(s) for advisory review and comment prior to submission for publication. Collaborator(s) will have 30 days (or as specified in the CTA) from the date of receipt for review. Press releases and other media presentations must also be forwarded to DCP prior to release. Each Party agrees to provide proposed press releases that reference or rely upon the work under this MTRA to the other party for review and comment at least seven business (7) days prior to publication. Copies of any manuscript, abstract, and/or press release/ media presentation should be sent to the Protocol Information Office at [NCI\\_DCP\\[contact]](mailto:[contact]).

The Protocol Information Office will forward manuscripts to the DCP Project Officer for distribution to the Collaborator(s). No publication, manuscript or other form of public disclosure shall contain any of Collaborator's confidential/proprietary information.

## **13. STATISTICAL CONSIDERATIONS**

### **13.1 Study Design/Description**

This is a Phase II, randomized, single-blind study with 2 intervention arms. A total of 108 DCIS participants will be consented and screened for eligibility and, with a conservative estimate, 48 (45%) participants are expected to be HLA-A2 positive. These 48 participants will be randomized 2:1 to vaccine and GM-CSF alone groups. Accounting for 10% attrition rate while on study and for approx. 5% non-evaluable sample rate, we expect to have 40 evaluable participants, 27 in vaccine and 13 in GM-CSF alone group, that have all baseline, post-vaccination (pre-surgery), and post-surgery measures of nelipepimut-S-specific CTL. With 27 and 13 in vaccine and GM-CSF alone groups, respectively, we will have 82% power to detect an effect size of 1 on the change of nelipepimut-S-specific CTL ("1 month (+/- 7 days) after completion of the vaccination series timepoint" minus pre-1st vaccine) between the two groups, corresponding to change of  $0.05\% \pm 0.05\%$  in vaccine group and  $0 \pm 0.05\%$  in control group, using two-sided t-test with a significance level of 0.05.

The decision rule for declaring the agent promising will be if we detect an effect size of 1 on the change of nelipepimut-S-specific CTL, and if there are not greater than 10% grade III AEs attributed to the active

study drug or IV AEs of any attribution. Completion of the current study will provide the necessary data to determine the next phase of study, specifically whether a subsequent, larger phase II will be conducted versus a phase III study.

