### **13.7 Evaluation of Toxicity**

All participants will be evaluable for toxicity from the time of their first vaccination. The toxicity profile in terms of type, attribute, and grade of toxicities will be described in each of the treatment arms.

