### **13.8 Evaluation of Response**

All randomized and treated participants are assessed for response to intervention including participants with protocol deviations. For the primary endpoint of change in the number of neli pepimut-S-CTL for an individual participant between the pre-vaccination timepoint and the 1 month (+/- 7 days) after surgery timepoint, "evaluable" will be defined as completing all pre-surgical vaccinations and all post-surgical vaccinations up to the 1 month (+/- 7 days) timepoint. However, the response outcome for both the evaluable and the non-evaluable participants will be computed and compared. For the safety endpoint, participants who receive at least one vaccination will be included in the safety evaluation. For the biomarker (biologic efficacy) endpoints, all non-compliant participants will be analyzed according to the intent-to-treat principle. All levels of compliance will be included in the full evaluation of endpoints if paired biopsies are available.

The primary endpoint is defined as the change in the number of E75-CTL for an individual participant between the pre-vaccination timepoint and the 1 month (+/- 7 days) after surgery.

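### The toxicity limit for declaring the agent promising (13.1) does not count grade V events, and leaves its unit, base and pooling of grades unstated

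*Combined protocol and SAP*

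**What the plan says.** The rule for declaring the agent promising appears once, in 13.1. It has an immunological part (an effect size of 1 on CTL change) and a toxicity part: "and if there are not greater than 10% grade III AEs attributed to the active" followed by "study drug or IV AEs of any attribution".

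The severity table in 11.1.3 lists five grades. Grade 5 stands on its own as "Death related to AE".

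Other sections bear on toxicity but do not mention the 10%:

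- 13.7: "All participants will be evaluable for toxicity from the time of their first vaccination", and "The toxicity profile in terms of type, attribute, and grade of toxicities will be described in each of the treatment arms".
- 13.8: "For the safety endpoint, participants who receive at least one vaccination will be included in the safety evaluation". This set covers both arms.
- 13.1, on numbers: "These 48 participants will be randomized 2:1 to vaccine and GM-CSF alone groups", with "27 in vaccine and 13 in GM-CSF alone group" expected to be evaluable for the CTL endpoint.

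**The concern.** The toxicity part names two classes of event: grade III if attributed to the active drug, and grade IV whatever the cause. A fatal event falls in neither. The rule is therefore stricter about a life-threatening event of any cause than about a death, even a death attributed to study drug. That ordering is unlikely to be intended.

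The sentence also leaves its calculation open. It speaks of a percentage of AEs, not of women. It gives no denominator and no arm for grade IV. It does not say whether the two classes are added before comparison with 10% or compared separately.

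The result informs whether a larger phase II or a phase III study follows. Under 6.9.2 the statistician and investigators are not blinded, so whoever settles the open points after the fact may already know which choice passes.

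**Working it through.** **The plan's own figure.** The only derived figure in 13.1 is the power. With 27 and 13 women, effect size 1 and a two-sided t-test at 0.05, the noncentrality parameter is 1/√(1/27 + 1/13) on 38 degrees of freedom. This gives 82.3%, against the stated 82%. The 10% toxicity limit comes with no denominator, count or operating characteristics, so there is nothing to reproduce for it.

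**Inputs.** 48 randomised at 2:1 gives 48 × 2/3 = 32 in the vaccine arm. This number is derived, not stated, and assumes all 32 receive at least one inoculation. One woman is 1/32 = 3.1 percentage points. The limit passes at 3/32 = 9.4% and fails at 4/32 = 12.5%.

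**Grade V.** Take four different vaccinated women: two with grade III attributed to study drug, one with grade IV, one with grade V.

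- As worded: (2 + 1)/32 = 3/32 = 9.4%, pass.
- With grade V counted: (2 + 1 + 1)/32 = 4/32 = 12.5%, fail.

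The same reversal occurs with the 27 evaluable women as base: 2/27 = 7.4% passes and 3/27 = 11.1% fails.

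**One death alone.** 1/32 = 3.1%. This passes whether or not grade V is counted.

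**Pooled or separate limits.** The largest number of affected women that still passes, if no woman is in both classes under separate limits:

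| Base | One pooled 10% | 10% for each class |
|---|---|---|
| 32 (vaccine arm, derived) | 3 (9.4%) | 6 (18.8%) |
| 27 (vaccine arm, evaluable) | 2 (7.4%) | 4 (14.8%) |
| 48 (all randomised) | 4 (8.3%) | 8 (16.7%) |
| 40 (all evaluable) | 4 (10.0%) | 8 (20.0%) |

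**Chance of passing with 32 women.** The pooled limit uses the exact binomial, P(X ≤ 3). Separate limits use the exact multinomial with at most 3 in each class, assuming that each affected woman has one worst grade and that grades III and IV are equally likely.

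| True rate of affected women | Pooled | Separate |
|---|---|---|
| 10% | 60% | 86% |
| 19% | 12% | 39% |

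**The case against.** The best reply is that the intended meaning is plain. One 10% governs two classes joined by a single conjunction, so a pooled limit is the natural reading. A percentage of grade III AEs is common shorthand for the percentage of patients with one, and the background sections report earlier toxicity by participant. The reference to the active study drug, which 6.7 sets against the control, ties the grade III class to the vaccine. Sections 13.7 and 13.8 supply a safety set. Deaths would not go unnoticed: 5.6 halts inoculations for serious adverse reactions including death, 11.2 requires prompt reporting, and the DSMB in 12.4 reviews toxicity. The phase II trials described in 2.3 and 6.2 had no grade 4 or 5 events, so the limit may never bind.

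Much of this stands. It makes the pooled, per-woman, vaccine-arm reading the one to expect, and it lowers the practical risk. But 5.6, 11.2 and 12.4 govern conduct, reporting and monitoring, and 13.7 and 13.8 govern description and the analysis set. None says what counts towards the 10%, and none adds grade V to it.

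Three stronger inferences go beyond the documents:

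- A reader might infer that the rule lets a regimen affecting 19% of women through. That needs separate limits, no woman in both classes, and exactly 32 vaccinated. The natural reading stops at 3/32.
- A reader might infer that the arm is wholly undefined, or that vaccine-arm cases would be divided by all 48 women. The grade III class points to the vaccine, and no section proposes 48 as the base. Only the arm for grade IV and the denominator are open.
- A reader might infer that a share of all AEs was meant, and estimate how many events could pass. The documents give no expected total of AEs per woman for this trial, so any such figure would be an assumption.

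**Conclusion.** The concern holds for grade V. As worded, the toxicity limit omits fatal events, and this can turn a fail into a pass: 9.4% against 12.5% in the four-woman case. The reversal is narrow. It occurs only when the other counted women already sit at the limit, and it assumes a count of women in a vaccine arm of 32. The omission does not mean that counting grade V would make any single death fail the rule. At 3.1% it would not, so the handling of deaths needs its own statement.

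The unstated unit, denominator, grade IV arm and pooling are secondary. Alone they would be close to missing detail, because a natural reading exists. They belong in the same repair because pooling roughly halves the largest number of affected women that passes (3 instead of 6 of 32).

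**What to change.** Reword the toxicity part of 13.1 so that the limit is the proportion of vaccine-arm women with at least one inoculation who had one or more events that are grade III attributed to study drug, or grade IV or V of any attribution. Count each woman once, and require that the proportion not exceed 10%. Show the same proportion for the GM-CSF arm beside it. Add a sentence in which the sponsor states how any death enters the declaration.

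The cost is one or two sentences. Grade and attribution are already required data elements in 11.1.2, deaths are reportable under 11.2, and no further participants are needed.

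The downside is a rule that is harder to pass. The change is slight if one pooled limit was intended. It is larger if separate limits were intended: under the assumptions above, the chance of passing falls from 86% to 60% at a true rate of 10%. The sponsor should therefore confirm that pooling was meant before the data are analysed.
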